8.3.3.3 EXPECTEDNESS

The principal investigator will be responsible for determining whether an adverse event (AE) is expected or unexpected. An AE will be considered unexpected if the nature, severity, or frequency of the event is not consistent with the risk information previously described for the study intervention.

8.3.4 TIME PERIOD AND FREQUENCY FOR EVENT ASSESSMENT AND FOLLOW-UP

The occurrence of an adverse event (AE) or serious adverse event (SAE) may come to the attention of study personnel during study visits and interviews of a study participant presenting for medical care, or upon review by a study monitor.

All AEs including local and systemic reactions not meeting the criteria for SAEs will be captured on the appropriate case report form (CRF). Information to be collected includes event description, time of onset, clinician's assessment of severity, relationship to study product (assessed only by those with the training and authority to make a diagnosis), and time of resolution/stabilization of the event. All AEs occurring while on study must be documented appropriately regardless of relationship. All AEs will be followed to adequate resolution.

Any medical condition that is present at the time that the participant is screened will be considered as baseline and not reported as an AE. However, if the study participant's condition deteriorates at any time during the study, it will be recorded as an AE.

Changes in the severity of an AE will be documented to allow an assessment of the duration of the event at each level of severity to be performed. AEs characterized as intermittent require documentation of onset and duration of each episode.

The principal investigator or study staff will record all reportable events with start dates occurring any time after informed consent is obtained until 7 (for non-serious AEs) or 30 days (for SAEs) after the last day of study participation. At each study visit, the investigator will inquire about the occurrence of

AE/SAEs since the last visit. Events will be followed for outcome information until resolution or stabilization.

In Uganda, the sponsor has taken out clinical trials insurance policy to cover compensation for any personal injury resulting from participants taking the study medication and/or study procedures, provided such personal injury is not due to fault or negligence of the study doctor or his team.

8.3.5 ADVERSE EVENT REPORTING

Adverse events will be reported to the University of Minnesota Institutional Review Board annually, at the time of continuing review, in accordance with their reporting policy.

8.3.6 SERIOUS ADVERSE EVENT REPORTING

All serious adverse events that meet the University of Minnesota Institutional Review Board's prompt reporting requirements will be reported to the IRB no later than 5 business days. All SEAs will also be reported to the JCRC IRB within 5 business days of awareness.

8.3.7 REPORTING EVENTS TO PARTICIPANTS

Not applicable.

8.3.8 EVENTS OF SPECIAL INTEREST

Not applicable.

8.3.9 REPORTING OF PREGNANCY

Not applicable.

8.4 UNANTICIPATED PROBLEMS

8.4.1 DEFINITION OF UNANTICIPATED PROBLEMS (UP)

The Office for Human Research Protections (OHRP) considers unanticipated problems involving risks to participants or others to include, in general, any incident, experience, or outcome that meets all of the following criteria:

- Unexpected in terms of nature, severity, or frequency given (a) the research procedures that are described in the protocol-related documents, such as the Institutional Review Board (IRB)-approved research protocol and informed consent document; and (b) the characteristics of the participant population being studied;
- Related or possibly related to participation in the research ("possibly related" means there is a reasonable possibility that the incident, experience, or outcome may have been caused by the procedures involved in the research); and
- Suggests that the research places participants or others at a greater risk of harm (including physical, psychological, economic, or social harm) than was previously known or recognized.

8.4.2 UNANTICIPATED PROBLEM REPORTING

The investigator will report unanticipated problems (UPs) to the University of Minnesota Institutional Review Board (IRB) and JCRC IRB per the UMN IRB's and JCRC IRB's prompt reporting requirements.

8.4.3 REPORTING UNANTICIPATED PROBLEMS TO PARTICIPANTS

Not applicable.

9 STATISTICAL CONSIDERATIONS

9.1 STATISTICAL HYPOTHESES

- Primary Efficacy Endpoint(s):

Null hypothesis: There is no difference in peak yellow fever antibody titer between individuals from the US and Uganda.

Alternative hypothesis: There is a difference in peak yellow antibody titer.

- Secondary Efficacy Endpoint(s):

Null hypothesis: There is no difference in baseline LN architecture measures (TZ collagen, FRCn, B cell follicles and populations, Tfh cells, and B Cell activating factor) between individuals from the US and Uganda. Alternative hypothesis: There are differences in these measures between the two countries.

Null hypothesis: There is no association between baseline measures of LN architecture and rate of YFV antibody decay. Alternative hypothesis: There are associations between these measures and rate of antibody decay.

Null hypothesis: Principal components of pathseq data are not associated with country of origin.

Alternative hypothesis: Some principal components of pathseq data are be associated with country.

Null hypothesis: There are no difference in helminth infection patterns between the US and Uganda.

Alternative hypothesis: Differences in helminth infections exist between the two countries.

Null hypothesis: Pathseq principal components with strong loadings for infection organisms are not associated with baseline measures of LN architecture. Alternative hypothesis: PC components with strong loadings for infectious organisms are associated with baseline LN architecture measures.

Null hypothesis: Presence of helminth infection is not associated with baseline LN architecture measures. Alternative hypothesis: Presence of helminth infection is associated with baseline LN architecture measures.

Null hypothesis: There is no association between changes in immune function after vaccination and measures of LN architecture. Alternative hypothesis: There is an association between change in immune function and measures of LN architecture.

Null hypothesis: There is no association between CD4, CD8 functional variables and CD4 subsets and peak YFV antibody titers or rate of antibody decay. Alternative hypothesis: There is an

association between CD4, CD8 functional variables and CD4 subsets and peak YFV antibody titers and rate of antibody decay.

Null hypothesis: There is no association between CD4, CD8 functional variables and CD4 subsets and peak specific IgM, IgG1, IgG2, IgG3 and IgG4 responses or rate of change. Alternative hypothesis: There is an association between CD4, CD8 functional variables and CD4 subsets and peak specific IgM, IgG1, IgG2, IgG3 and IgG4 responses or rate of change.

Null hypothesis: There is no change in immune activation or inflammation measures or CD4 and CD8 cells after immunization. Alternative hypothesis: There is a change in immune activation or inflammation measures or CD4 and CD8 cells after immunization.

9.2 SAMPLE SIZE DETERMINATION

We will enroll 30 individuals from Uganda and 16 individuals from the US. With this sample size our study will have more than adequate power to test our primary aim, differences in peak antibody titers between countries. Assuming yellow fever antibody titers show a similar range as in our previous studies (a standard deviation of 1 log) for both populations we have over 85% power to detect a difference in peak antibody titers of 1 log, with a two-sided test with alpha level of 0.05. This calculation is based on comparison to a T distribution with 43 degrees of freedom.

Since, in fact, we will be using a Mann-Whitney U test for this comparison we also illustrate that this sample size is sufficient using power simulations. For all simulations we assume that the Ugandan population will have a mean of 7.89 log titers and approximate standard deviation of 1 and the Minnesota population has a mean of 8.89 and an approximate standard deviation of 1. One thousand iterations were conducted for each simulation scenario. As is illustrated in the table below we will have over 84% power for a variety of distributional assumptions

Distribution	Uganda parameters	MN parameters	Power
Normal	$\mu=7.89, \sigma=1$	$\mu=8.89, \sigma=1$	0.871
Gamma	$k=62.25, \theta=0.13$	$k=79.03, \theta=0.11$	0.874
T + shift	$v= 20, \text{shift}=7.89$	$v= 20, \text{shift}= 8.89$	0.841

9.3 POPULATIONS FOR ANALYSES

For comparisons involving the primary endpoint, YFV titers, we will only include study participants who received the YF vaccine. For analysis of secondary endpoints, we will use data from all available study participants.

9.4 STATISTICAL ANALYSES

9.4.1 GENERAL APPROACH

Medians and interquartile ranges will be presented for descriptions of continuous data. Percentages will be presented for categorical data.

Counts of cell frequency and QIA endpoints involving the percent area will be log-transformed and linear regression analyses will be conducted where appropriate. If there are no detectable cells or there is no staining detected for a large portion of study participants logistic regression modeling will be conducted, instead, with presence or absence of the measure being the outcome.

Two-sided tests will be conducted for all comparisons. Subjects specific random effects will be included in all mixed effects models and permutation p-values will be presented. To control for multiple comparisons, a cut-off of alpha=0.01 will be used for determining statistical significance of all secondary endpoints.

Measures which have non-zero coefficients in lasso models will be considered to be associated with the outcome. Measures which have non-zero correlation coefficients after applying sparse canonical correlation analysis will be considered to be correlated with the outcome measure.

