9.4.3 ANALYSIS OF THE SECONDARY ENDPOINT(S)

Differences in rate of YFV antibody titer decay will be compared between vaccinated Ugandans and Minnesotans using linear mixed effects regression model with measurement time, country, and the interaction between measurement time and country as predictors. Baseline LN measures (area with collagen, area with desmin staining, frequency and size of B cell follicles, and frequency of Tfh cells) will be compared between the two countries using Mann-Whitney U tests.

We will examine the association between vaccine response over time and baseline LN measures using linear mixed effects models adjusting for measurement time and gender.

To examine differences in infection patterns between the two countries, we will perform principal component analyses on the baseline pathseq data. We will test for differences in infection patterns between Uganda and the US populations using logistic regression with country as the outcome and the scores for each of the first five principal components as predictors. Differences in helminth infections between Ugandans and Minnesotans will be compared using Fisher's exact test.

We will examine the association between infection history and baseline LN architecture by fitting separate linear regression models for each measure of baseline LN architecture with gender and the 5 pathseq principal component scores as predictors. The association between helminth infections and baseline LN architecture measures will be assessed using Mann-Whitney U tests.

To elucidate the role of previous infections on inflammation and activation we will use sparse canonical correlation analysis (Reference: Witten, D., Tibshirani, R., & Hastie, T. (2009). A penalized matrix decomposition, with applications to sparse principal components and canonical correlation analysis. *Biostatistics*, 10(3), 515-534.) to identify sets of organismal sequences correlated with baseline measures of systemic and lymphatic inflammation (plasma cytokines, frequency of TGF β + and TNF+ cells in lymphoid tissues) and immune activation (Ki67+ and CD69 + cells). The association between helminth infection and measures of inflammation and activation be assessed using a logistic lasso regression model. Measures which have non-zero coefficients in the model will be considered associated with helminth infection.

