The association between change in measures of CD8 function (IFN γ , TNF α , and IL-2) after vaccination and measures of LN architecture will be examined by fitting mixed effects linear models using area with collagen staining, area with desmin staining, and measurement time and gender as predictors.

The association between immune function after vaccination and measures of inflammation and activation will be assessed using separate lasso regression for each measure of immune function (antigen specific CD4, CD8 function measures, and CD4 and CD8 subpopulations). Inflammation and activation measures which have non-zero coefficients in the model will be considered predictive of immune function.

We will examine the impact of measures of immune function on YFV response using separate mixed effects linear models with gender, measurement time and measures of immune function (antigen specific CD4, CD8 functional variables, or CD4 and CD8 subpopulations) as predictors. Similar models will be fit for YF specific IgM, IgG1, IgG2, IgG3 and IgG4 responses.

The impact of vaccination on measures of inflammation and activation be assessed using mixed effects repeated measures model with gender, measurement time, and vaccination status as predictors. To assess the impact of vaccination on CD4 and CD8 cells in LT similar models will be fit, but only gender and vaccination status (measurement taken before or after vaccination) will be used as predictors.

Missing data will not be imputed and a significance level of 0.01 will be used for secondary analyses due to the large number of hypotheses to be tested. The results from all of these investigations will be reported so that the reader can assess the effect of multiple hypothesis testing.

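### Sections 9.4.1 and 9.4.3 count any non-zero sparse-CCA or lasso coefficient as an association, with no penalty rule and no null reference

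*Combined protocol and SAP*

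**What the plan says.** Section 9.4.1 (General Approach) sets two decision rules. For lasso: "Measures which have non-zero coefficients in lasso models will be considered to be associated with the outcome". For sparse CCA: "Measures which have non-zero correlation coefficients after applying sparse canonical correlation analysis will be considered to be correlated with the outcome measure".

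Section 9.4.3 (Analysis of the Secondary Endpoints) uses them in three places:

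- Sparse CCA of pathseq organisms against inflammation and activation markers, "to identify sets of organismal sequences correlated with baseline measures of systemic and lymphatic inflammation" and with immune activation. The method is cited to a paper titled "A penalized matrix decomposition, with applications to sparse principal components and canonical correlation analysis".
- A logistic lasso for helminth infection: "Measures which have non-zero coefficients in the model will be considered associated with helminth infection".
- A separate lasso for each immune-function measure: "Inflammation and activation measures which have non-zero coefficients in the model will be considered predictive of immune function".

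Two other sentences in Section 9.4.1 bear on error control: "To control for multiple comparisons, a cut-off of alpha=0.01 will be used for determining statistical significance of all secondary endpoints", and "Subjects specific random effects will be included in all mixed effects models and permutation p-values will be presented". Section 9.4.3 adds that all results will be reported so that readers can judge multiplicity.

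Neither section says how a penalty is chosen or how many canonical components are kept. Neither gives a permutation, stability or hold-out check for these two methods. Section 9.1 lists no null hypothesis for any of the three analyses, yet they stand in the secondary section and not in Section 9.4.9 (Exploratory Analyses).

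**The concern.** Lasso and sparse CCA are selection tools. A non-zero coefficient means that the variable survived a given penalty. It carries no error rate until the penalty rule is known and the fit is compared with what noise would give. The 0.01 cut-off cannot supply this, because these rules produce no p-value.

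These analyses decide which organisms and markers are reported as linked to inflammation, helminth infection and immune function. The link from endemic infection to inflammation is central to the study hypothesis (Section 2.1), and sparse CCA is the tool assigned to it. If that link were absent, the rule as written would still name organisms and markers as correlated. For lasso, an analyst could choose among penalty rules with very different error rates after seeing the data, and still comply with the plan.

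**Working it through.** **Plan's own figures.** The only operating characteristic the plan computes is power for the primary comparison (Section 9.2: 30 v 16, difference 1 log, SD 1 log, two-sided 0.05). It reproduces: a noncentral t with 43 degrees of freedom gives 0.884 (stated: over 85%), and a Mann-Whitney simulation with normal data gives 0.861 (stated: 0.871). The plan gives no such figure for sparse CCA or lasso.

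**Inputs.**
- n = 30 + 16 = 46 (Sections 9.2 and 9.3), an upper limit.
- 17 markers: the 13 plasma cytokines of the preliminary data in Section 2.2, plus TGFβ+, TNF+, Ki67+ and CD69+ cells. That the same panel will be used is an assumption.
- 50 or 200 organisms, and 12 of 46 participants with helminths: assumptions, since the documents give neither.

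**Sparse CCA, by structure.** Penalized matrix decomposition maximises u'X'Yv with u and v held to unit length and bounded in L1 norm. Unless X'Y is exactly zero, neither u nor v can be all zero. The non-zero rule therefore always flags at least one organism and one marker, and the L1 bound only sets how many.

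**Sparse CCA, by simulation.** In null data with the L1 bound at 0.1 to 0.7 of √p (8 settings, 500 datasets each), both sides were flagged in every dataset.
- Mean organisms flagged: about 1 to 39 of 50, or about 4 to 157 of 200.
- Mean in-sample canonical correlation from noise: about 0.41 to 0.93.
- Zero-inflated, skewed organism data with correlated markers (4 settings) also gave 100%.

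**Comparator at the plan's 0.01.** Testing every organism-marker pair at 0.01, treated as independent:
- 50 × 17 = 850 tests: 1 − 0.99^850 = 0.9998 chance of flagging something. With 200 × 17 = 3400 tests it is about 1.
- Chance that a given organism is flagged: 1 − 0.99^17 = 0.157. Expected organisms flagged: 50 × 0.157 = 7.9, or 200 × 0.157 = 31.
- Simulation gave the same: about 100% of datasets, with 7.9 of 50 or 31 of 200 organisms.

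**Linear lasso, 17 measures, null data.** Chance of at least one non-zero coefficient per fit:

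| Penalty rule | Any false selection |
|---|---|
| Minimum cross-validation error | 39-41% |
| One standard error (1-SE) | 2-4% |
| BIC | 9% |
| AIC | 57% |
| Fixed 0.2 (standardised data) | 97% |
| Fixed 0.4 (standardised data) | 6% |

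The comparator is 17 independent tests at 0.01, or 15.7%. Per measure, minimum-CV gives 9% and 1-SE gives 0.7%, against 1%.

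**Logistic lasso.** With 12 of 46 infected, minimum-CV gives 38-42% and 1-SE gives 3-5%. Across other assumed settings, 1-SE ranged up to 15%.

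**Check of a permutation gate in null data.** With sparse CCA (200 organisms, 17 markers, fixed penalty, 99 permutations), p ≤ 0.01 occurred in 2 of 150 datasets (1.3%). With re-tuning in each of 199 permutations, rejections were 1 of 120 (pooled sparse CCA) and 6 of 400 (linear lasso).

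**The case against.** The strongest objection concerns the 100%. A reader might infer that sparse CCA is far worse than the plan's own standard because it declares something in every null dataset. The documents do not support that. Section 9.4.1 sets 0.01 per test with no limit on any false finding, and pairwise testing at that level also flags something in essentially every null dataset. A tight sparse-CCA penalty flags fewer organisms than those tests, and a loose one flags more. This objection stands, and the 100% is not the defect.

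A reader might also infer that the plan leaves open whether both countries are pooled. Section 9.3 uses all available participants for secondary endpoints, and Section 9.4.3 gives no country term or stratum for these analyses. The plain reading is pooled and unadjusted.

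Other defences carry less weight:

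- The permutation p-values could be meant to cover these methods. The sentence is about mixed models, and the following paragraph still makes non-zero the criterion.
- Reporting everything helps readers count analyses, but it gives no null reference for a selected variable.
- The analyses may be meant as selection only; identifying sets is selection language, and Section 9.1 has no hypothesis for them. Even so, the plan places them among secondary analyses and words the results as correlated, associated and predictive.

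The evidence for the gate is also thin. One rejection in 120 has an exact 95% upper limit of 4.6%, so it is compatible with 1% without establishing it.

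**Conclusion.** The point holds. For sparse CCA, the stated rule cannot return a negative result, and an unstated penalty sets how many variables are flagged. For lasso, a negative result is possible, but the false-selection rate is undefined: about 40% per null fit under minimum-CV and about 2-4% under 1-SE for a linear model with 17 measures.

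It does not follow that lasso selection is unsound in itself. Under 1-SE, the linear lasso roughly meets the plan's 0.01 per-measure standard. That statement is firm only for the linear model, because logistic 1-SE figures ran from about 3% to 15% with the settings.

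The structural result rests on the norm-constrained method that the plan cites; a formulation that can return all zeros would behave differently. The counts rest on the assumed numbers of markers and organisms and the assumed helminth prevalence.

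Because the analyses are pooled, a selected link may reflect the difference between Uganda and Minnesota. Section 4.2 attributes that difference to endemic infection, so pooling can be defended if it is reported as such.

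Reach is limited. None of the three analyses has antibody titer as its outcome, and the primary Mann-Whitney test and ordinary secondary tests are unaffected. The change should be made before these analyses are run.

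**What to change.** 1. Pre-specify the penalty rule for each lasso and sparse-CCA analysis, and the number of canonical components.
2. Call a result an association only if a permutation p-value for the whole fit (for example the canonical correlation, or the cross-validated lasso error) is at most 0.01, with the penalty re-tuned in every permutation. State the statistic and the number of permutations. Otherwise label the analysis exploratory selection.
3. In either case, label individually selected organisms and markers as exploratory, because a p-value for the whole fit does not validate each one.
4. Report the results as pooled over countries. A within-country analysis is an optional sensitivity analysis.

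If no test is wanted, the minimum is to state the penalty rule and the number of components and to label all three analyses exploratory.

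The cost is SAP wording and computing time. The downside is that fewer measures will be called associated and moderate signals will often miss the gate. In rough simulations (50 datasets per setting for sparse CCA, 80 for linear lasso), the share reaching 0.01 was:

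- Pooled sparse CCA, 5 of 200 organisms linked to 3 markers: 82% at pairwise correlation 0.6 (interval about 69-91%) and 12% at 0.36.
- Linear lasso with one true marker: 14%, 43% and 66% at correlations 0.4, 0.5 and 0.6.
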